7.2.2 Hypoglycemia

Hypoglycemia will be regarded as an AE and recorded and documented on an AE form (and SAE form, if applicable).

Hypoglycemia is defined as a decline in plasma glucose to below 70 mg/dL (3.9 mmol/L). However, in the time period from initiation of the hypoglycemic clamp procedure (see Section 8.2.3.1) until 45 minutes after dosing, hypoglycemia is defined as a decline in plasma glucose to below 45 mg/dL (2.5 mmol/L).

During the dosing visit, prior to administration of the IMP, a plasma glucose value of <45 mg/dL (2.5 mmol/L) will be treated by an IV glucose solution. After administration of the IMP in the period from 8 minutes until 44 minutes after dosing, a plasma glucose value of <45 mg/dL (2.5 mmol/L) will be treated by an IV glucose solution, and if a plasma glucose value of \geq 70 mg/dL (3.9 mmol/L) is not achieved within the 45 minutes after IMP administration, IV glucose infusion will also be initiated.

If the subject experiences symptoms of hypoglycemia, a plasma glucose measurement should be taken in order to classify the event (please refer to Section 7.4.2 for additional details).

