Plasma glucose concentrations will be measured using the US FDA-approved glucose analyzer YSI 2300, Yellow Springs Instruments, Yellow Springs, OH or the Super GL analyzer, [name] GmbH, Freital, Germany. After the start of the insulin infusion, plasma glucose will be measured approximately every 10 minutes while plasma glucose is above 110 mg/dL, and approximately every 5 minutes once plasma glucose is at or below 110 mg/dL.

Once the glucose concentration declines to <60 mg/dL (3.3 mmol/L), the insulin infusion will be stopped, and 5 min later plasma glucose concentration will be measured at the glucose analyzer and blood samples for baseline assessment of plasma glucose, dasiglucagon/GlucaGen PK, and insulin PK will be collected. The samples are the baseline samples and should be collected within 2 minutes before IMP administration.

- If plasma glucose is ≥ 45 mg/dL and < 60 mg/dL (2.5-3.3 mmol/L), study treatment (IMP) will be administered, defining time, $t=0$. The study treatment will be delivered in the abdomen, buttock, or thigh (according to stratification) via SC injection.
- If plasma glucose is < 45 mg/dL (2.5 mmol/L), IV glucose solution will be administered sufficient to raise plasma glucose to within the 45-60 mg/dL target range. The run-in period will be adequately extended (at least 30 min) until the above target is achieved and new baseline samples for plasma glucose, dasiglucagon/GlucaGen PK, and insulin PK will be collected. Glucose should not be infused within 10 minutes before IMP administration. If plasma glucose is not within target range after the second attempt, the subject should be rescheduled for a new treatment visit within 7 days (+ 2 days).

Administration of IMP should not occur earlier than 9:00 hours in the morning or later than 12:00 hours.

As shown in **Table 4**, serial blood samples for glucose will be collected at $t=0, 4, 6, 8, 10, 12, 15, 17, 20, 25, 30, 40, 50, 60, 75$ and 90 minutes post-dosing. Samples for assessing

plasma dasiglucagon/GlucaGen concentration will be collected at t=0, 15, 30, 35, 40, 50, 60, 90, and 120 minutes. Samples for assessing plasma insulin concentration will be collected at t=0, 30, and 60 minutes.

Table 4 Post-treatment blood sampling times

Times	0	4	6	8	10	12	15	17	20	25	30	35	40	50	60	75	90	120
Plasma glucose	Y	Y	Y	Y	Y	Y	Y	Y	Y	Y		Y	Y	Y	Y	Y	Y	
PK Dasiglucagon/ GlucaGen	Y						Y				Y	Y	Y	Y	Y		Y	Y
PK Insulin	Y										Y			Y				

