Refer to Section [7.2.7](#) for details of laboratory safety sampling and to Section [7.4.2](#) for details of blood glucose safety sampling.

When the t=90-minute blood sampling for plasma glucose has been collected the subjects are allowed to eat moderately. Drinking of water is allowed *ad libitum* during the entire procedure.

Hypoglycemia Rescue Provisions

During insulin-induced hypoglycemia, plasma glucose levels will be monitored closely at site for safety reasons as described in Section [7.4.2](#). Subjects should receive post-treatment rescue glucose infusion to ameliorate persistent hypoglycemia, as follows.

1. Glucose infusion should be initiated if a subject experiences severe alarming escalation of symptoms of hypoglycemia (e.g. symptoms suggesting a change in consciousness) at any time during the trial; glucose infusion should be initiated targeting a plasma glucose levels >70 mg/dL.
2. If plasma glucose is <45 mg/dL (2.5 mmol/L) between t=8 and t=44 minutes, rescue glucose infusion (1-2 mg/kg administered IV over about 5 seconds) should be initiated to maintain plasma glucose between 45 mg/dL and 55 mg/dL (2.5-3.1 mmol/L). Pause glucose infusion if plasma glucose is >55 mg/dL.
3. If plasma glucose is <70 mg/dL at t=45 minutes, rescue glucose infusion (2-3 mg/kg administered IV over about 5 seconds) should be initiated to maintain plasma glucose between 70 mg/dL and 80 mg/dL (3.9-4.4 mmol/L). Pause glucose infusion if plasma glucose is >75 mg/dL (4.2 mmol/L).

Subjects should remain in bed until completion of the test procedure 300 minutes after dosing (bathroom visits are allowed).

The IMP will be administered SC according to Section 6.3. The time of IMP administration will be recorded. At the timepoint when the insulin infusion is stopped, the total insulin dose which was required to induce hypoglycemia will be recorded.

AEs will be specifically recorded during the procedure at several timepoints.

The investigator must provide information to the subjects on how to resume their usual diabetes treatment.

The subject may be released from the clinical center if the investigator does not have any safety concerns based on the last safety plasma glucose value and the general condition of the subject. However, at the discretion of the investigator or on request of the subject, the subject may stay at the trial center for a longer period.

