9.5.2 Primary confirmatory endpoint

Time to plasma glucose recovery. Plasma glucose recovery is defined as first increase in plasma glucose of ≥ 20 mg/dL (1.1 mmol/L) from baseline during the hypoglycemic clamp procedure without administration of rescue IV glucose.

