9.5.2.1 Primary analysis

The primary endpoint will be summarized using Kaplan-Meier (KM) estimates stratified by treatment group and injection site. The treatment group difference between dasiglucagon and placebo will be evaluated inferentially using a pairwise two-sided log-rank test.

In the primary analysis, recovery cannot be achieved in those subjects where IV glucose treatment is administered. Those subjects who receive IV glucose will be censored (i.e. set to ‘not recovered’) at 45 minutes after dosing.

In sensitivity analyses, the time to plasma glucose recovery will be analyzed 1) without censoring for those subjects who require rescue IV glucose before 45 minutes and 2) with censoring at the time of administration of rescue IV glucose before 45 minutes.

The primary endpoint will additionally be analyzed using a Cox proportional hazards (CPH) time to event statistical model, if the hazards by treatment group can be assumed proportional using a graphical comparison of log-minus-log survival curves and no more than two-thirds of the recovery times are censored in each treatment group. The CPH model will be used for inferences, with treatment group and injection site modeled as categorical effects, and baseline plasma glucose modeled as a continuous covariate. The treatment group rate ratios, active versus placebo, will be estimated together with the 95% confidence intervals, and pairwise treatment group inferences (dasiglucagon vs placebo, GlucaGen vs placebo) will be evaluated using two-sided likelihood ratio tests.

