9.5.3.1 Confirmatory analysis

The key secondary incidence variables (plasma glucose recovery within 30 minutes, within 20 minutes, within 15 minutes, within 10 minutes, in hierarchical order for inference) will be analyzed using descriptive statistics (frequency and percentage) by treatment group. Inferential treatment group comparisons will be assessed via pairwise tests of independent binomial proportions (dasiglucagon versus placebo, GlucaGen versus placebo) using Fisher’s exact test for each pairwise comparison.

The key secondary endpoints of plasma glucose CFB within 30 minutes, within 20 minutes, within 15 minutes, and within 10 minutes after study drug injection or at the time of rescue, will be analyzed with the plasma glucose CFB at rescue carried forward in those subjects who require rescue IV glucose before plasma glucose ≥ 20 mg/dL recovery. Each of these CFB variables will be analyzed using an Analysis of Covariance model, with treatment group modeled as a fixed effect and with the baseline plasma glucose modeled as a covariate. The dasiglucagon versus placebo treatment group difference will be evaluated inferentially as a least squares means contrast, using a two-sided t-test at the

0.05 significance level, first for the 30 minute CFB, and then sequentially for the 20 minute, 15 minute, and 10 minute variables, until the first failure to reject.

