9.9 Subject withdrawals and missing data

Failure is defined for the primary time-to-recovery endpoint as censored with time to recovery set to the maximum follow-up time, here 45 minutes. Individuals will be set to 'failure' in case of receiving rescue IV glucose, discontinuation due to treatment or discontinuation in connection with the induced hypoglycemia state. Only if an intermediate assessment is missing independent of rescue treatment, study treatment or an adverse event including hypoglycemia, interpolation can be applied to impute a missing value.

The same construct of imputation applies for the analysis of the plasma glucose AUC0-30min.

In the case of subject withdrawal, no imputation of values for PK or PD measurements will be done. Analyses will be done on valid cases only, i.e., no imputation techniques such as last observation carried forward will be applied.

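### The primary rule makes any IV glucose recipient not recovered without requiring that the glucose came before recovery, so a recovery already observed can be erased by rescue at 45 minutes

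*Protocol*

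**What the plan says.** The points below refer to the current version of the Protocol. The same file holds superseded versions with other censoring rules, which are not counted here.

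- **Endpoint (9.5.2).** Recovery is the first rise of at least 20 mg/dL "from baseline during the hypoglycemic clamp procedure without administration of rescue IV glucose". The order of rescue and rise is not stated.
- **Primary analysis (9.5.2.1, repeated in the synopsis).** "recovery cannot be achieved in those subjects where IV glucose treatment is administered". It continues: "Those subjects who receive IV glucose will be censored", meaning set to not recovered, at 45 minutes after dosing.
- **Missing data (9.9).** A subject is a failure "in case of receiving rescue IV glucose, discontinuation due to treatment" or discontinuation linked to the induced hypoglycemia. Again no order is given.
- **General efficacy section (9.5).** It gives a different primary rule: rescued subjects are censored at their time to recovery.
- **Rescue provisions (8.2.3.1).** "If plasma glucose is <70 mg/dL at t=45 minutes, rescue glucose infusion" should be started, whatever rise has already occurred. Glucose may also be given for severe symptoms at any time in the trial.
- **Change-from-baseline endpoints (9.5.3.1).** These are analysed "with the plasma glucose CFB at rescue carried forward in those subjects who require rescue IV glucose before plasma glucose" has risen by the 20 mg/dL that defines recovery. Here the order is explicit.
- **Sensitivity analyses (9.5.2.1).** Both vary the handling of rescue before 45 minutes only.

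**The concern.** Recovery is defined by a relative rise, whereas rescue at 45 minutes is defined by an absolute level. The two can both be true of the same subject. When they are, the rule lets a treatment given at 45 minutes overwrite an event that was observed earlier, so the primary outcome depends on what happens after the event. Because the change-from-baseline endpoints carry the ordering condition and the primary endpoint does not, a programmer could reasonably treat the omission as deliberate.

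At stake are the event count and the estimated effect in the primary confirmatory test. Section 9.5 adds a second, incompatible rule, so the primary derivation is not uniquely fixed.

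**Working it through.** **1. Can a recovered subject be rescued at 45 minutes?** Section 8.2.3.1 allows dosing at a baseline b of at least 45 and below 60 mg/dL. Recovery needs a level of at least b + 20, and rescue at 45 minutes needs a level below 70.

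- Both hold with no decline at all if b + 20 < 70, that is b < 50. Example: 46 to 67 mg/dL is a rise of 21, hence a recovery, yet 67 < 70 triggers rescue.
- At b of 50 or more, recovery means a level of at least 70, so the subject must fall back below 70 by 45 minutes. This can also happen from lower baselines.

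**2. Do the sensitivity analyses restore these subjects?** No. The first lifts the censoring, and the second moves it to the time of rescue, but both apply to rescue before 45 minutes. Recoveries followed by rescue at 45 minutes stay failures.

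**3. The plan's own power.** Inputs from section 9.1: exponential medians of 10 and 20 minutes, 78 and 39 subjects, 45 minutes of follow-up, two-sided 5%.

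- Expected events = 78 × (1 − 2^−4.5) + 39 × (1 − 2^−2.25) = 74.6 + 30.8 = 105.4.
- Schoenfeld power = Φ(√(105.4 × 2/3 × 1/3) × ln 2 − 1.96) = Φ(3.354 − 1.960) = 0.918.
- Simulated log-rank test, 3,000 runs: 0.903.

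The stated 90% reproduces and is not in dispute.

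**4. Effect of recoding.** A share q of recoveries was set to not recovered at 45 minutes (1,500 runs per scenario, medians 10 and 20). The Protocol gives no value for q, so every q is an assumption.

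| Where recoveries are recoded | q | Power | Apparent rate ratio (Peto-type) |
|---|---|---|---|
| none | 0 | 0.903 | 1.90 |
| both arms | 5% | 0.805 | 1.76 |
| both arms | 10% | 0.701 | 1.68 |
| both arms | 20% | 0.487 | 1.54 |
| both arms, only recoveries after 20 min | 20% | 0.871 | 1.88 |
| both arms, only recoveries after 20 min | 50% | 0.807 | 1.82 |
| placebo only | 5% | 0.954 | 2.07 |
| placebo only | 10% | 0.979 | 2.25 |
| placebo only | 20% | 0.997 | 2.61 |
| dasiglucagon only | 5% | 0.665 | 1.63 |
| dasiglucagon only | 10% | 0.359 | 1.40 |

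Ten percent on placebo alone is about 3 subjects.

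A separate simulation on the planned sampling times (1,500 runs) gave 0.892, 0.785 and 0.699 at q = 0, 5% and 10% in both arms. With a placebo median of 30 minutes it gave 1.00, 0.994 and 0.978.

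**5. Type I error (2,000 runs, both medians 20 minutes).** Equal recoding of 10% gives a rejection rate of 0.048, so the test holds its level if the arms behave alike throughout. If times to recovery are equal but 10% of placebo recoveries alone are recoded, the rate is 0.14. The test would then be picking up the later glucose course, not time to recovery.

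**6. The 45-minute trigger itself.** Section 7.2.2 starts glucose if at least 70 mg/dL "is not achieved within the 45 minutes after IMP administration, IV glucose infusion will also be initiated". Section 8.2.3.1 looks at the level at 45 minutes. A subject who reached 72 and fell to 66 is rescued under 8.2.3.1 but not under 7.2.2. Which recoveries get overwritten therefore also depends on which wording a site follows.

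**The case against.** The strongest objection is that such cases will be rare on dasiglucagon. Section 2.1.3.1 reports that every phase 2 subject, at all doses, both reached 70 mg/dL and rose by at least 20 mg/dL within 30 minutes, with a median time to peak concentration of 35 minutes. This stands. A reader might infer that the rule mainly penalises the active arms and costs power; the document does not support that. Small, slow rises still below 70 at 45 minutes are at least as plausible on placebo, where recoding raises power and inflates the effect.

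Other stronger readings also fail:

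- **One third of subjects affected.** The interval 45 to 50 is one third of the permitted baseline range (5 of 15 mg/dL). That is a width, not a share of subjects, and the clamp targets 55 mg/dL.
- **Pre-dose glucose counts as failure.** Section 8.2.3.1 does foresee it: "IV glucose solution will be administered sufficient to raise plasma glucose to within the 45-60 mg/dL target range". Section 9.5.2.1 omits the word rescue, but 9.5.2 and 9.9 use it, 8.2.3.1 describes rescue as post-treatment, and new baseline samples follow pre-dose glucose. This limb rests on loose wording only.
- **Responder endpoints are distorted too.** Their windows end at 10 to 30 minutes, and the 9.5.2.1 rule is stated for the primary analysis. Carry-over of rescue at 45 minutes is not established.

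It can also be said that the definition in 9.5.2 naturally means no rescue up to the rise, and that the statistical analysis plan may refine details. But 9.5.2.1 and 9.9 are the operative rules and are categorical. This is a rule stated wrongly, not a detail left open.

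**Conclusion.** The point holds in limited form. As written, the primary rule can turn an observed recovery into a failure because of glucose given afterwards. The Protocol's own 45-minute trigger makes this possible, and neither sensitivity analysis undoes it. Section 9.5 contradicts the rule.

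The number affected and the direction of the bias cannot be determined from the document. Assuming equal recoding and medians of 10 and 20 minutes, power falls from about 0.90 to 0.80 at 5% and 0.70 at 10%. The loss is smaller if only late recoveries are hit. Recoding mainly on placebo inflates the apparent rate ratio, for example from about 1.9 to 2.3 at 10%. Section 9.1 expects a placebo median above 20 minutes; at 30 minutes, power stays at about 98-99% under equal recoding of 5-10%. So this is not evidence that the trial is underpowered, nor that the rule is safely conservative. It should be corrected before unmasking because it defines the primary event and is cheap to correct.

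**What to change.** In the synopsis, 9.5.2.1 and 9.9, state that only rescue IV glucose given after dosing and before the first rise of at least 20 mg/dL sets a subject to not recovered, censored at 45 minutes. State also that IV glucose given before dosing, or started after recovery, leaves recovery status unchanged. Replace the rule in 9.5 with the same sentence. Use the same ordering for the 10-, 15-, 20- and 30-minute responder endpoints, for consistency.

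Separately, the 45-minute rescue triggers in 7.2.2 and 8.2.3.1 must be reconciled. No clinical rule is proposed here.

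The cost is one sentence in four places, a matching line for the responder endpoints, and derivation code. No new data are needed: time to first rescue infusion is already a safety endpoint in 3.5.

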9.5.3 Secondary endpoints

- Plasma glucose recovery within 30 minutes, within 20 minutes, within 15 minutes, and within 10 minutes after study drug injection without administration of rescue IV glucose.
- Plasma glucose changes from baseline within 30 minutes, within 20 minutes, within 15 minutes, and within 10 minutes after study drug injection or at the time of rescue.

9.5.3.1 Confirmatory analysis

The key secondary incidence variables (plasma glucose recovery within 30 minutes, within 20 minutes, within 15 minutes, within 10 minutes, in hierarchical order for inference) will be analyzed using descriptive statistics (frequency and percentage) by treatment group. Inferential treatment group comparisons will be assessed via pairwise tests of independent binomial proportions (dasiglucagon versus placebo, GlucaGen versus placebo) using Fisher’s exact test for each pairwise comparison.

The key secondary endpoints of plasma glucose CFB within 30 minutes, within 20 minutes, within 15 minutes, and within 10 minutes after study drug injection or at the time of rescue, will be analyzed with the plasma glucose CFB at rescue carried forward in those subjects who require rescue IV glucose before plasma glucose ≥ 20 mg/dL recovery. Each of these CFB variables will be analyzed using an Analysis of Covariance model, with treatment group modeled as a fixed effect and with the baseline plasma glucose modeled as a covariate. The dasiglucagon versus placebo treatment group difference will be evaluated inferentially as a least squares means contrast, using a two-sided t-test at the

0.05 significance level, first for the 30 minute CFB, and then sequentially for the 20 minute, 15 minute, and 10 minute variables, until the first failure to reject.

9.5.4 Secondary clinical efficacy (PD) endpoints

- Time to first plasma glucose concentration of ≥ 70 mg/dL (3.9 mmol/L) without administration of rescue IV glucose.
- Plasma glucose response as area under the curve above baseline from time zero to 30 minutes, $AUC_{0-30min}$.

Secondary clinical efficacy endpoints will be assessed based on plasma concentration data from samples collected at the dosing visit (Visit 2).

Unless otherwise stated, the population base of analysis will be the FAS.

9.5.4.1 Analysis of secondary clinical efficacy (PD) endpoints

1. Time to first plasma glucose concentration ≥ 70 mg/dL from baseline. This time-to-event endpoint will be evaluated using a Kaplan-Meier approach, with treatment group as a stratification factor, analogous to that used for the primary endpoint analysis. Differences between the KM curves (dasiglucagon versus placebo, GlucaGen versus placebo) will be evaluated inferentially using pairwise two-sided log rank tests. If the ≥ 70 mg/dL endpoint is not met within 45 minutes post-dosing, the time of the last valid plasma glucose measurement up to 45 minutes will be the censoring time.
2. The AUC will be calculated as the baseline-adjusted area under the plasma glucose profile over time:
 - a. $AUC_{0-30min}$: restricting the time window to the 0 to 30 minutes interval.
3. The log-transformed AUC endpoint will be analyzed using an analysis of covariance (ANCOVA) model with treatment as fixed effect and baseline plasma glucose modeled as a covariate. The least squares means treatment group differences will be back-transformed (anti-logged) for presentation as a ratio of the treatment group geometric means, with their corresponding 95% CI.

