The key secondary endpoints of plasma glucose changes from baseline (CFB) within 30 minutes, within 20 minutes, within 15 minutes, and within 10 minutes after study drug injection or at the time of rescue, will be analyzed with the plasma glucose CFB at rescue carried forward in those subjects who require rescue IV glucose before plasma glucose ≥ 20 mg/dL recovery. Each of these CFB variables will be analyzed using an Analysis of Covariance model, with treatment group modeled as a fixed effect and with the baseline plasma glucose modeled as a covariate. The dasiglucagon versus placebo treatment group difference will be evaluated inferentially as a least squares means contrast, using a two-sided t-test at the 0.05 significance level, first for the 30 minute CFB, and then sequentially for the 20 minute, 15 minute, and 10 minute variables, until the first failure to reject.

The continuous clinical efficacy variables, the exploratory variables, and the pharmacokinetics variables will each be summarized descriptively by treatment group. The clinical efficacy variables will be analyzed analogous to the plasma glucose CFB variables.

The safety analyses will include by-treatment-group descriptive summaries of vital sign measurements, laboratory measures (including immunogenicity incidence), physical examination assessments, rescue IV glucose (incidence and amount of glucose infused), and adverse events. The number and percentage of subjects reporting specific events, such as nausea and vomiting, will be presented by body system and preferred term.

Further details will be included in the Statistical Analysis Plan, to be completed before database lock and treatment unmasking.

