At the discretion of the investigator, additional plasma glucose measurements can be taken at any time during the trial, for example when there is a suspicion (e.g. symptoms) of a hypoglycemic episode.

Plasma glucose measurements for safety should only be recorded in the eCRF if they are related to an AE (e.g. a hypoglycemic episode).

In case of persistent post-treatment hypoglycemia, subjects will receive rescue treatment with an IV glucose infusion (see Section 8.2.3.1 for details). Blood samples for PD and PK assessments should still be taken at the specified timepoints.

7.4.3 *Plasma insulin measurements*

Samples for insulin assessment will be collected at the dosing visit (Visit 2, pre-dose and at 30 and 60 minutes after dosing). The actual time of blood sampling for evaluation of plasma insulin should not deviate from the nominal time by more than ± 1 minute. Pre-dose is defined as within 2 minutes prior to dosing.

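### The log-transformed analysis of baseline-adjusted glucose AUC0-30min has no defined value for placebo subjects whose glucose stays at or below baseline

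*Protocol*

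**What the plan says.** Section 9.5.4 defines the endpoint as "Plasma glucose response as area under the curve above baseline from time zero to 30 minutes" and adds "Unless otherwise stated, the population base of analysis will be the FAS". Section 9.5.4.1 gives the derivation, "The AUC will be calculated as the baseline-adjusted area under the plasma glucose profile over time", and then the model: "The log-transformed AUC endpoint will be analyzed using an analysis of covariance (ANCOVA) model", with treatment and baseline glucose as terms. Treatment differences are "back-transformed (anti-logged) for presentation as a ratio of the treatment group geometric means, with their corresponding 95% CI".

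The synopsis describes a different analysis: "The clinical efficacy variables will be analyzed analogous to the plasma glucose CFB variables". Those change-from-baseline (CFB) variables are analysed by an ANCOVA without a log transform and compared by a difference in LS means (section 9.5.3.1).

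On missing data, section 9.9 first defines failure for the primary endpoint, next allows interpolation of an intermediate sample that is missing for unrelated reasons, and then says: "The same construct of imputation applies for the analysis of the plasma glucose AUC0-30min". On rescue, section 7.4.2 says: "Blood samples for PD and PK assessments should still be taken at the specified timepoints". No section says how a zero or negative area is handled.

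**The concern.** A logarithm needs a positive argument, and a baseline-adjusted area need not be positive. The protocol's own procedure makes flat or falling placebo profiles possible:

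- Insulin is stopped only about 5 minutes before the baseline sample, and dosing requires glucose of at least 45 mg/dL (8.2.3.1).
- Rescue is foreseen for glucose under 45 mg/dL from t=8. A subject who meets that trigger has fallen below baseline.
- Type 1 diabetes was chosen to avoid an endogenous glucagon response (5.1).
- The placebo median time to a 20 mg/dL rise is expected to exceed 20 minutes (9.1).

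The subjects whose log is undefined are the poorest placebo responders. Excluding them departs from the FAS and raises the placebo mean. Replacing their values by a small constant lets that constant set the ratio. Very small positive areas have a similar pull on a geometric mean.

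**Working it through.** The plan gives no figure for the AUC analysis. The nearest stated figure is the 90% power of the primary log-rank test. (The file holds more than one protocol text; sections 9.1 and 9.9 are cited from the first.) Expected events by 45 minutes with exponential medians of 10 and 20 minutes are 78 × (1 − 2^(−4.5)) + 39 × (1 − 2^(−2.25)) = 74.55 + 30.80 = 105.35. Schoenfeld power is Φ(√(105.35 × 2/3 × 1/3) × ln 2 − 1.96) = Φ(1.39) = 91.8%; simulated log-rank power was 90.4%. The stated figure reproduces, and nothing below touches it.

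**One subject.** A steady fall from 55 to 45 mg/dL over 30 minutes has net area −10 × 30/2 = −150 mg·min/dL. Counting only area above baseline gives 0. Neither has a logarithm.

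**How many subjects.** The documents give no placebo profile, so a range is assumed: linear profiles, baseline 48-60 mg/dL, normally distributed slopes with SD 0.3-0.6 mg/dL/min, measurement noise SD 0-2 mg/dL, and trapezoidal area on the protocol's sampling times. For a linear profile, AUC0-30 = slope × 30²/2 = 450 × slope. Without noise, the share at or below zero is Φ(−mean/SD). For mean 0.3 this is Φ(−1) = 16% at SD 0.3 and Φ(−0.5) = 31% at SD 0.6. Simulation including noise gave:

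| Mean placebo slope (mg/dL/min) | Mean AUC (450 × slope) | Net area ≤0 | Of 39 | Above-baseline area exactly 0 |
|---|---|---|---|---|
| −0.3 | −135 | 69-84% | 27-33 | 44-84% |
| 0 | 0 | about 50% | 19-20 | 20-50% |
| 0.3 | 135 | 16-31% | 6-12 | 5-31% |
| 0.6 | 270 | 2-17% | 1-6 | 1-16% |
| 1.0 | 450 | 0-5% | 0-2 | 0-5% |

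A slope of 1.0 puts the median 20 mg/dL rise at 20/1.0 = 20 minutes, the limit that section 9.1 expects placebo to exceed. The lower slopes therefore fit the protocol's expectation, but it does not say how much lower.

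**What the handling does.** With an assumed active slope of 2.5 (SD 0.5), noise SD 1, and 78 against 39 subjects, the median dasiglucagon/placebo results over 400 simulated trials were:

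| Placebo slope, SD | Ratio: dropped | Ratio: floored at 1 | Ratio: floored at 0.01 | Ratio: above-baseline area, zeros dropped | Untransformed LS-mean difference |
|---|---|---|---|---|---|
| 0, 0.3 | 15 | 132 | 1347 | 39 | 1130 |
| 0.3, 0.3 | 8.3 | 18 | 37 | 11.7 | 990 |
| 1.0, 0.6 | 2.8 | 3.7 | 4.6 | 3.1 | 677 |

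The untransformed estimate recovers the assumed truth, 450 × (2.5 − placebo slope) = 1125, 990 and 675, and keeps all 117 subjects. In the middle row its 5th to 95th percentile range is 933-1051.

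**Near-zero values.** With 38 placebo subjects at 200 and one at 1, the placebo geometric mean is multiplied by exp((ln 1 − ln 200)/39) = 0.873, so a single subject lowers it by 13%.

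**The case against.** Several counter-arguments carry weight.

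- **Above-baseline reading.** If only area above baseline counts, negative values cannot occur, and a zero needs every sample at or below baseline. This is correct and weakens the point, but zeros and near-zeros remain, and the two descriptions of the area leave the reading open.
- **The count may be small.** At the 20-minute limit it is 0-2 of 39. This stands; rescue rules are safety contingencies and do not predict how often glucose falls.
- **The SAP may add a rule.** Section 9 allows this, and nowhere does the protocol say that such subjects are dropped. But it already fixes the log scale and the ratio, so an SAP could only exclude subjects, add a constant, or override the protocol.
- **Limited consequences.** The endpoint lies outside the testing hierarchy (9.5.1). All phase 2 subjects rose by at least 20 mg/dL within 30 minutes (2.1.3.1), so the dasiglucagon/GlucaGen ratio should be definable. Dropping poor placebo responders works against dasiglucagon. All of this stands.

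Two stronger readings may tempt a reader. The first is that section 9.9 applies the censored-at-45-minutes failure rule to an area, which is impossible, so the sentence should go. The sentence just before it concerns interpolating a missing intermediate sample, and that is the natural meaning of imputation there. It suits an AUC, and deleting it would remove a usable rule.

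The second is that rescue glucose substantially inflates the placebo area. Before 30 minutes, glucose-triggered rescue applies only from t=8 and aims for 45-55 mg/dL, while baseline lies between 45 and just under 60. Glucose held in that range is at most 55 − 45 = 10 mg/dL above baseline, and not above it at all if baseline is 55 or more. Even the extreme case, held at 55 from t=8, adds no more than 10 × 22 = 220 mg·min/dL. Only symptom-triggered rescue, which targets above 70 mg/dL, could add more. The rescue rule for the AUC needs stating, but the documents do not show a large distortion.

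**Conclusion.** The point holds for the log scale: sections 9.5.4 and 9.5.4.1 prescribe a transform that is undefined for outcomes the protocol's procedure permits, and the synopsis points to a different model. Of the two clinical efficacy endpoints, AUC0-30min is the only continuous one, so the synopsis sentence must be meant for it.

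The size is conditional on assumed linear placebo profiles: about 0-2 of 39 at the 20-minute limit, 6-12 at a mean slope of 0.3 mg/dL/min, and about half if placebo is flat. Where several subjects are affected, the choice of handling can move the ratio more than fourfold (8.3 to 37 at slope 0.3).

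The contrasts with placebo are mainly affected. If all three arms share one model, extreme placebo logs would also widen the interval for dasiglucagon against GlucaGen. A reader might infer that the trial's confirmatory conclusions are at risk. They are not: the primary analysis, the key secondaries, power and type I error control are untouched. This should be fixed, but the trial's main claim does not depend on it.

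**What to change.** 1. In 9.5.4.1, analyse AUC0-30min untransformed with the same ANCOVA (treatment, baseline glucose) in the FAS, and report the LS-mean difference with 95% CI. This also brings the section into line with the synopsis.
2. State there that area below baseline counts as negative.
3. In 9.5.5.1, write out the log transform, the ANCOVA and the back-transformation for PK AUC and Cmax. That section now borrows them by reference to the AUC method and would otherwise lose them.
4. In 9.9, keep interpolation of missing intermediate samples for the AUC and say so directly. Add that, for subjects rescued before 30 minutes, the change from baseline at rescue is carried forward in the AUC analysis, as section 9.5.3.1 already plans for the CFB endpoints. Make clear that the bar on carrying observations forward in 9.9 concerns withdrawal.

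The cost is wording in the protocol and SAP before unmasking, with no change to data collection or sample size. The downside is that the result is a difference in mg·min/dL and not a ratio.
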